## **EFFICACY ASSESSMENT**

Primary study endpoints: emerging atrial fibrillation, transient ischemic attack (TIA) or stroke, unstable angina, myocardial infarction, heart failure, coronary revascularization, cardiovascular death; Secondary study endpoints: decreased cardiac function with preserved ejection fraction; new cardiac remodeling; aortic aneurysm or aortic dissection; ECG showed that QTc (QT interval corrected by heart rate) was more than 500ms or QTc was longer than the baseline level for more than 60ms, emerging torsade de pointes ventricular tachycardia and other serious arrhythmias; the relationship between the deviations of blood pressure within the same day and the difference of cardiac function indexes.

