#### Exclusion criteria for hypertension:

- Secondary hypertension caused by renal parenchymal diseases, renal vascular diseases, coarctation of aorta and endocrine system diseases;
- (2) Severe cardiovascular and cerebrovascular diseases; heart valve disease; persistent atrial fibrillation and severe arrhythmia; previously undergone cardiovascular disease surgery;
- (3) Abnormal liver function; abnormal renal function and diabetes;
- (4) Pregnant or breastfeeding women;
- (5) Expected survival time due to non-cardiovascular disease<4 years;
- (6) Patients with poor echocardiographic image quality.

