#### **RESEARCH PLAN**

#### **Estimation of Sample Size**

Use PASS 11.0.7 software, bilateral inspections,  $\alpha = 0.05$ , with the incidence rate of cardiovascular adverse events in the left ventricular hypertrophy group was 4.9%, and the incidence rate of cardiovascular adverse events in the left ventricular non-hypertrophy group was 2.2%, at least 986 hypertensive patients were included in the left ventricular hypertrophy group and the left ventricular non hypertrophy group, respectively. Considering the 10% loss rate, at least 1085 patients were included. With 20 research centers, we planned to collect at least 110 patients with hypertension (including 55 patients in left ventricular hypertrophy group), 5-10 healthy volunteers (aged 30-60 years) in each center. Then 2200 patients with hypertension in total, and 100 healthy volunteers will be selected in this study.

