#### (2) Accessory examination

- 1) ECG examination: use resting ECG to evaluate arrhythmia and ST-T changes, etc.
- 2) Laboratory tests:

Fasting for more than 6 hours, blood routine, urine routine, fasting blood glucose, alanine aminotransferase, aspartate aminotransferase, blood urea nitrogen, creatinine, plasma total cholesterol, triglyceride, low-density lipoprotein cholesterol, high-density lipid Protein cholesterol, high-sensitivity C-reactive protein, prothrombin time, serum troponin, NT-proBNP.

3) Transthoracic echocardiography:

Two-dimensional dynamic images of left ventricular parasternal long axis, apical fourchamber heart, apical two-chamber heart, apical long axis, left ventricular apex level, papillary muscle level, and mitral valve level short-axis view; measure left ventricular ejection fraction (LVEF); Pulse wave Doppler was used to obtain the diastolic mitral valve orifice blood flow spectrum, and tissue Doppler was used to obtain the mitral valve annulus motion spectrum, and E/e' was calculated; Using speckle tracking imaging (STI) ultrasound technology to measure global longitudinal strain (GLS)/strain rate, global circumferential strain, global radial strain, global area strain (3D-GAS), left ventricular torsion, left ventricular rotation/untwisting speed, systolic dissynchrony index (SDI) and right ventricular free wall systolic peak strain (RVFWS) and so on.

4) Carotid ultrasound examination: the patient was the occipital supine position, with slightly raised jaw, the face was turned to one side, and the sternocleidomastoid muscle was fully exposed. The probe scans from the posterior edge of the sternocleidomastoid muscle to display the long axis and short axis images of the common carotid artery, internal and external carotid arteries, and bifurcation. The intima-media thickness, internal diameter and blood flow velocity were measured at 1-2 cm before the

bifurcation of the common carotid artery.

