## **DIAGRAM OF RESEARCH SCHEME**

## **CHART OF RESEARCH SCHEME**

Follow-up time	0 month	12th month	24th month	36th month	48th month
Information	•				
Medical history	•				
Inclusion Criteria	•				
Informed consent	•				
Electrocardiogram	•	•	•	•	•
Physical examination	•	•	•	•	•
Laboratory examination	•				
Echocardiography	•		•		•
Arterial ultrasound	•		•		•
Drugs treatments	•	•	•	•	•
Adverse events		•	•	•	•

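### The 500 ms limb of the secondary QTc endpoint has no baseline condition, so a patient already above 500 ms at entry can be counted as a follow-up event without any rise

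*Protocol*

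**What the plan says.** The secondary endpoints in the Protocol, EFFICACY ASSESSMENT, include an ECG item that is met when QTc "was more than 500ms or QTc was longer than the baseline level for more than 60ms". The same item goes on to "emerging torsade de pointes ventricular tachycardia and other serious arrhythmias", and the same list contains "new cardiac remodeling".

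The inclusion criteria for hypertension do not mention QTc. The only rhythm-related exclusion is "persistent atrial fibrillation and severe arrhythmia". Under Accessory examination, the stated use of the ECG is to "use resting ECG to evaluate arrhythmia and ST-T changes, etc".

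In the CHART OF RESEARCH SCHEME, the row "Electrocardiogram" is marked at months 0, 12, 24, 36 and 48, so a baseline tracing is planned for every patient. The Estimation of Sample Size section sets the cohort size: "Then 2200 patients with hypertension in total, and 100 healthy volunteers will be selected in this study".

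**The concern.** An endpoint observed over follow-up should record something that happens during follow-up. The second limb does this by comparing each tracing with baseline. The first limb is an absolute threshold with no such comparison, and the limbs are joined so that either is enough. A patient who enters above the threshold and stays above it meets the endpoint with no change, or even after an improvement.

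The surrounding wording suggests that new occurrence is what the list is after: remodeling is qualified as new, and torsade de pointes as emerging. The 500 ms limb carries no such word.

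The study is a non-randomised cohort whose hypertensive patients are grouped by baseline cardiac configuration. Nothing in the design balances baseline QTc across those groups. If baseline prolongation differs between them, the difference would pass into the observed frequency of this item and look like a difference in follow-up events.

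**Working it through.** **Inputs.** From the Protocol: thresholds of 500 ms and 60 ms (EFFICACY ASSESSMENT), ECGs at month 0 and at four annual visits (CHART OF RESEARCH SCHEME), and 2,200 hypertensive patients (Estimation of Sample Size). The Protocol gives no QTc mean, SD or prevalence of prolongation, so there is no figure of its own to reproduce. Every QTc value below is an assumption.

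**Step 1: the rule.** Let B be baseline QTc and F a follow-up QTc, in ms.

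- As written: event if F > 500, or F − B > 60.
- With a baseline condition on the first limb: event if (F > 500 and B ≤ 500), or F − B > 60.

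The two rules differ in one situation only: B > 500, F > 500 and F − B ≤ 60.

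**Step 2: illustrative records.**

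| B | F | F − B | As written | With baseline condition |
|---|---|---|---|---|
| 510 | 504 | −6 | event | no event |
| 520 | 505 | −15 | event | no event |
| 510 | 510 | 0 | event | no event |
| 490 | 505 | +15 | event | event |
| 430 | 495 | +65 | event | event |
| 510 | 575 | +65 | event | event |

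The first three rows are prolongation carried over from entry. New crossings of 500 ms and rises above 60 ms count under both rules.

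**Step 3: does anything else in the Protocol close the gap?** The inclusion and exclusion criteria give no QTc limit. The severe-arrhythmia exclusion does not name a prolonged interval, and the stated use of the ECG does not include a QTc check at entry.

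**Step 4: how many patients could start above 500 ms?** With a normal distribution, the expected number is 2,200 × P(Z > (500 − mean)/SD).

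- Mean 425, SD 20: z = 75/20 = 3.75, P = 0.00009, giving 0.2 patients.
- Mean 430, SD 25: z = 70/25 = 2.80, P = 0.0026, giving 5.6 patients.
- Mean 435, SD 30: z = 65/30 = 2.17, P = 0.0151, giving 33.3 patients.

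**Step 5: how many of them would be counted wrongly?** Some patients above 500 ms at baseline drop below it at every later visit, so the counts shrink. I simulated one baseline and four follow-up ECGs with no true change and a within-patient SD of 12 to 15 ms. I then counted patients with B > 500, at least one F > 500 and no rise above 60 ms. Per 2,200 patients this gives fewer than 0.1, about 2 to 3, and about 22 to 25 in the three cases. Loss to follow-up would lower these further.

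**The case against.** **Entry criteria.** The strongest defence is that the endpoint puts QTc prolongation in the same item as torsade de pointes and other serious arrhythmias. On that grouping, the exclusion of severe arrhythmia might already keep such patients out. This is a possible reading, and in practice some sites may apply it. But a prolonged interval is not itself named as an arrhythmia, and no QTc value appears in the criteria, so the text does not secure it.

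**Follow-up framing.** The chart records adverse events from month 12 onward, and the follow-up section asks for the time at which an event occurred. Both suggest that events are meant to arise in follow-up. That supports the intended meaning, but the event list in that section omits QTc, so it does not repair the definition. A statistical analysis plan, not shown here, could remove patients who already meet the criterion from the risk set. It would then be narrowing a definition that the Protocol has already fixed with numbers.

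**Stronger readings that a reader might infer.** The documents do not support these:

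- *The same patient is scored again at each visit.* No count of recurrent events is described. The event analysis in the Protocol is Cox regression on event time.
- *The hypertrophy comparison is inflated.* The Cox, ROC and reclassification analyses stand under the main endpoint events. No hypertrophy contrast on the QTc item is specified, and the Protocol does not say whether baseline prolongation is more frequent with hypertrophy.
- *A given share of all QTc events is spurious.* Any such share would rest on an assumed QTc distribution and on assuming no true events. Real events would lower it.

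**Consequence.** It is fair to say that this matters little. The QTc criterion is one component of several secondary endpoints, and an absolute threshold beside a change threshold is a legitimate choice. What stands is narrower: the absolute limb needs a baseline condition if it is to describe a follow-up event.

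**Conclusion.** The point holds as a minor defect in a definition. As written, a patient above 500 ms at month 0 who is still above 500 ms at a follow-up ECG meets the secondary QTc endpoint even if QTc has not risen, and no entry criterion explicitly prevents this.

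The size is unknown from the Protocol. Under the three assumed distributions it runs from practically nobody to about 33 of 2,200 starting above the threshold, with fewer wrongly counted. Whether this biases a comparison between configuration groups, and in which direction, depends on whether baseline prolongation differs between them. Neither the primary endpoint nor the sample size depends on this item.

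**What to change.** Reword the first limb as: QTc more than 500 ms at follow-up in a patient whose baseline QTc was 500 ms or less. Keep the limb for a rise of more than 60 ms over baseline for all patients, and list patients above 500 ms at baseline separately, by configuration group.

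The cost is one clause. The month-0 ECG is already scheduled, so no new data are needed. The downside is that a few prevalent cases leave the event count; the separate listing keeps them visible. The change concerns only how the endpoint is scored, not how any patient is managed.

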#### **RESEARCH PLAN**

#### **Estimation of Sample Size**

Use PASS 11.0.7 software, bilateral inspections,  $\alpha = 0.05$ , with the incidence rate of cardiovascular adverse events in the left ventricular hypertrophy group was 4.9%, and the incidence rate of cardiovascular adverse events in the left ventricular non-hypertrophy group was 2.2%, at least 986 hypertensive patients were included in the left ventricular hypertrophy group and the left ventricular non hypertrophy group, respectively. Considering the 10% loss rate, at least 1085 patients were included. With 20 research centers, we planned to collect at least 110 patients with hypertension (including 55 patients in left ventricular hypertrophy group), 5-10 healthy volunteers (aged 30-60 years) in each center. Then 2200 patients with hypertension in total, and 100 healthy volunteers will be selected in this study.

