### Inclusion criteria for hypertension:

- (1) Age 30-75 years old;
- (2) No antihypertensive drugs were used and three blood pressure measurements were conducted on different days, with systolic blood pressure ≥ 140 mmHg (1 mmHg=0.133 kPa) and/or diastolic blood pressure ≥ 90 mmHg; or have a history of hypertension and are using antihypertensive drugs, even if the blood pressure is lower than 140/90 mmHg;
- (3) Left ventricular ejection fraction was normal (LVEF  $\geq 0.5$ ).
- (4) All patients agreed to participate in the experiment and signed the informed consent form.

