## (3) Group analysis:

1) For the healthy volunteers and hypertensive patients enrolled in the group: between 9:00

a.m. and 17:00 p.m. on the day of enrollment, at an interval of more than 4 hours, the patients performed two echocardiographic examinations in a calm state, measured and recorded their blood pressure at the same time (three measurements at an interval of 1-2 minutes), and measured the indicators at the two baseline levels on the day of enrollment. The changes of left ventricular global longitudial strain (GLS) and myocardial work (MW) in hypertension and healthy volunteer were compared, and the correlation between them and the changes of blood pressure was analyzed;

2) Analysis for hypertensive patients with different left ventricular configurations: configuration analysis was conducted based on the left ventricular remodeling standards recommended by ASE/EACVI 2015 guidelines and the EMINCA study combined with Ganau classification. Hypertensive patients were divided into normal left ventricular configuration group, left ventricular remodeling group, left ventricular eccentric hypertrophy group and left ventricular concentric hypertrophy group. Baseline, 12months, 24months, 36months and 48months echocardiography images were recorded and analyzed, compared the cardiac structure and functional indicators, and recorded clinical adverse events;

(2) Analysis for hypertensive patients with different left atrial configurations: according to the abnormal threshold of left atrial enlargement recommended by ASE/EACVI 2015 guidelines and the standard of Chinese left atrial enlargement recommended by EMNICA study, hypertensive patients were divided into normal left atrial group and left atrial enlargement group. Baseline, 12months, 24months, 36months and 48months echocardiography images were recorded and analyzed, compared the cardiac structure and functional indicators, and recorded clinical adverse events.

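### Healthy volunteers stop at age 60 but patients run to 75, and the comparison of same-day GLS and myocardial work changes is neither restricted to shared ages nor adjusted for age

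*Protocol*

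**What the plan says.** Two different age ranges are fixed in the Protocol.

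- Estimation of Sample Size sets the volunteers at "5-10 healthy volunteers (aged 30-60 years) in each center", and states that "100 healthy volunteers will be selected in this study". The definition of healthy volunteers under Groups adds no age matching.
- Inclusion criteria for hypertension, item 1, reads "Age 30-75 years old". Item 2 also admits treated patients: "or have a history of hypertension and are using antihypertensive drugs".

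Statistical Treatment, (3) Group analysis, item 1, covers the volunteers and the hypertensive patients enrolled. On the enrolment day, "at an interval of more than 4 hours, the patients performed two echocardiographic examinations in a calm state", with blood pressure taken at the same time. Two analyses follow. The first is the group comparison: "The changes of left ventricular global longitudial strain (GLS) and myocardial work (MW) in hypertension and healthy volunteer were compared". The second, a separate step in the same item, relates these to blood pressure: "the correlation between them and the changes of blood pressure was analyzed". Neither an age restriction nor an age adjustment is attached to the group comparison. The regression methods in section (4) concern cardiovascular events and the factors behind remodeling and atrial enlargement, not this comparison.

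Efficacy Assessment lists as a secondary endpoint "the relationship between the deviations of blood pressure within the same day and the difference of cardiac function indexes". That matches the correlation, not the contrast between patients and volunteers.

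**The concern.** The comparison is meant to show how hypertension relates to the same-day change in GLS and myocardial work. As specified, the patient group can include people up to 75 and the volunteer group cannot include anyone above 60, so an age difference between the groups is likely by design. If the within-day change depends on age, part of the observed contrast is an age effect presented as a hypertension effect.

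There is a possible route for this. Under Myocardial work parameters, the work indices are computed from the patient's blood pressure, and the Background links GLS to afterload. If within-day blood pressure change differs with age, it would carry into the change in these indices.

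An age term in a model would not fully solve it: above 60 there are no volunteer data, so such a model could only extrapolate from volunteers aged 60 or younger.

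**Working it through.** **The plan's own figures.** The Protocol gives no sample size or precision for the volunteer comparison. Its only sizing, 986 per group for 4.9% versus 2.2% events, concerns patients alone. The pooled two-proportion formula, two-sided 0.05, gives 985 at 90% power (the power is inferred, not stated). That sizing does not bear on this point.

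**Inputs from the Protocol.** Volunteers: 100, ages 30-60. Patients: 2,200, ages 30-75.

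**Assumptions, not document figures.** All 2,200 patients contribute. The SD of the within-day change is equal in both groups. Patients up to 60 have the same mean age as the volunteers (midpoint 45). Patients above 60 average 67.5 (midpoint of 60-75). The share above 60 is 20%, one third or 50%; one third is what uniform ages would give (15/45).

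**Step 1: standard error as planned**, in units of the SD of the change: sqrt(1/100 + 1/2200) = 0.1022.

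**Step 2: mean age gap** = share above 60 × (67.5 − 45) = share × 22.5 years.

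**Step 3: break-even slope**, the age effect on the within-day change at which the bias equals one standard error = 0.1022 / (gap in decades).

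**Step 4: standard error after restriction to ages 30-60** = sqrt(1/100 + 1/patients remaining).

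| Share above 60 | Age gap (years) | Break-even slope (SD per decade) | Patients remaining | SE after restriction | Rise |
|---|---|---|---|---|---|
| 20% | 4.5 | 0.1022/0.45 = 0.227 | 1,760 | 0.1028 | 0.5% |
| 33% | 7.5 | 0.1022/0.75 = 0.136 | 1,467 | 0.1034 | 1.1% |
| 50% | 11.25 | 0.1022/1.125 = 0.091 | 1,100 | 0.1044 | 2.2% |

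**What one standard error means.** A bias of that size raises the false-positive rate of a two-sided 5% test to P(Z > 0.96) + P(Z < −2.96), about 17%. With no age effect on the change, the bias is zero.

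Precision barely moves because the 100 volunteers dominate the standard error.

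**The case against.** **This belongs in the SAP.** The two age ranges describe different populations and do not contradict each other, and analysis-set restrictions and covariates are commonly left to the SAP. That is fair as far as adjustment goes. But the Protocol itself fixes the volunteers' upper age limit and applies the comparison to everyone enrolled, and no SAP model can supply volunteers above 60.

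**No error is demonstrated.** This stands in part. Each person is examined twice on one day, so stable age differences in the level of GLS or myocardial work cancel. The Background's remark that age affects normal values concerns left ventricular mass, a level, not a same-day change. A reader might infer that the comparison is biased; the documents do not support that, only that the design leaves it open.

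**Stronger readings that fail.**
- A reader might take the group contrast for a listed secondary endpoint. Efficacy Assessment lists the blood pressure relationship, which is the separate correlation.
- A reader might infer from the single month-0 echocardiography mark in the Chart of Research Scheme that only a small subset is examined twice, which would make restriction costly. A visit chart does not count examinations within a day, and Group analysis, item 1, applies the double examination to enrolled volunteers and patients.
- A reader might limit the blood pressure correlation to patients. Neither section does so, and the fix must not narrow it.

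**Age is only one difference.** True: the groups also differ in, for example, antihypertensive drug use, and the comparison stays observational after the change.

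**Conclusion.** The concern holds as a minor point. The mismatch in age ranges and the unrestricted, unadjusted comparison are plain in the text; the size of any resulting bias is unknown and may be zero. Under the assumed age shares, an age effect of roughly 0.09 to 0.23 SD of the within-day change per decade would be enough to produce a bias of one standard error. One standard error is a chosen benchmark, and the age distribution and equal SDs are assumptions. The primary event analyses use hypertensive patients and are untouched. Restricting to shared ages is a cheap improvement rather than the repair of a demonstrated error.

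**What to change.** In Statistical Treatment, (3) Group analysis, item 1, add:

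*The comparison of same-day changes in GLS and MW between hypertensive patients and healthy volunteers will use patients aged 30-60 years and will be adjusted for age and sex; same-day changes in patients above 60 years will be described without a volunteer contrast.*

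Leave the correlation with blood pressure changes as it stands, for volunteers and for patients of all ages.

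Cost: no new data and no change to recruitment, since age and gender are already collected under Clinical data. As a protocol modification it needs Ethics Committee approval (Ethics; Quality Control, item 9). The downside is that there is no volunteer contrast above 60, plus the small loss of precision worked out above. Raising the volunteers' upper age limit would be an alternative, but it needs new recruitment.

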#### The main test indicators in the selection and follow-up period

#### (1) Clinical data

1) Demographic characteristics: name, hospitalization number/outpatient number, gender, age, nationality, occupation, address, postal code, telephone number;

2) Baseline clinical data: blood pressure, body mass index, smoking history, drinking history, medication history, family history (smoking is defined as continuous or

cumulative smoking for 6 months or more in a lifetime);

- 3) Routine physical examination;
- 4) Medication history: antihypertensive drugs, statins, aspirin, etc.

